### Sample size

We aim to recruit 15-20 patients to test the feasibility of the intervention in this population.

### Inclusion criteria

For the purpose of this study service users eligible for the study are:

- (a) Aged 65 years and older

- (b) Cognitive capacity to provide informed consent
- (c) Attending Older adult mental health services
- (d) MH team deem client stable and able to participate in intervention
- (e) Patient independently mobile and living in the community (may use a walk aid)(Clinical frailty Scale  $\leq 5$ )

### Exclusion Criteria

For the purpose of this study

- (a) Service users with moderate advanced dementia will be excluded as the intervention is unsupervised.
- (b) Patients who cannot provide informed consent
- (c) Patients that cannot understand English or require a translator
- (d) Patients experience acute mental health crisis
- (e) Patients with significant restricted mobility, using Zimmer frame inside or outside their house (CFS $\geq 5$ )

### Study Design

The study uses a one group pretest –posttest intervention design with patient survey at baseline, 1 month and 3 month follow-up. The project is undertaken over 12 months. Once ethical approval is obtained, patient recruitment and baseline data is collected and the intervention delivered: in March – June 2023, 1 month follow-up April to July and three month follow-up August to October 2023.

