#### Data collection

The ANP completes the structured questionnaire with the patient in the MH clinic or patient home during routine clinical consultations. The one-month and three month follow-up via telephone or in the OPD clinic/persons' home as part of normal schedule of visits. No extra clinic or home visits are planned as part of the study.

The structured questionnaire used in this study has been developed by an expert group of geriatricians, and old age psychiatry and includes validated measures of frailty (see below)

This study tests the user acceptability of the intervention and the recruitment and data collection approach.

Ethical approval was obtained from Clinical Research Ethics Committee of the Cork Teaching Hospitals (CREC)

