In the past week (7 days) have you completed the exercises on the information leaflet

Frequency (None=0, 1 day=1, 2 days=2; 3 days=3, 4 days=4, 5 days=5); X Duration (none =0; 10 mins=1, 11-20 mins=2, 21-30 mins=3, >30 mins=4). Higher values indicate greater exercise intensity (min score 0 to 20).

Nutrition: Simplified nutritional appetite questionnaire (SNAQ) is a four item scale (rate appetite, When I eat I feel full, food tastes, normally I eat) are rated on a five point scale (1 to 5). Total possible score range from 5 to 20, higher scores indicate better appetite. SNAQ score 14 indicates significant risk of at least 5% weight loss within six months (Kruizenga et al., 2005).

Protein intake: Patients self-reported the number of protein portions eaten in the previous day: Protein was categorised as: meat/fish; milk/dairy; eggs/cheese; vegetable protein

The one-month questionnaire focused on acceptability of intervention and ease of use.

Patients are also be asked to give qualitative feedback on the intervention.

The 3-month questionnaire repeated the baseline measures and adherence questions.

Implementation outcomes:

Acceptability (Bespoke item)

One item measures acceptability: The exercise and nutrition advice was acceptable to me (made sense) rated on a 5 point Likert scale (1=strongly disagree to 5 strongly agree)

Ease of Use (Bespoke item)

One item measured Ease of Use ' To what extent was it easy to incorporate the exercise and nutrition advice into your daily routine rated on a five point Likert scale (1=very difficult to 5 very easy)

Recommend to others (bespoke item)

The final item sought participants opinion on 'recommending the intervention to others. 'In your opinion, should we continue to offer this advice and information leaflets to other people attending our service? With three response options Yes/No/ Don't know

A study log is maintained recording the number of eligible patients invited to participate, the number of patients who refused, reasons for refusal, number of patients who consented, number of patients who completed 1-month and 3-month follow-up.

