### Data management

Data is collected using a paper questionnaire. The data collector is not blinded to the study intervention.

Each participant is allocated a study ID that links the study register maintained by clinical site to the questionnaire data. The patient ID file will be stored separately from the Research data with a Participant ID used to link the two files. The excel sheets are stored in a password protected PC in the HSE in a locked office facility. Paper questionnaires are stored in a locked filing cabinet on the clinical site in the HSE facility

Only de-identified data using a Study ID is shared with UCC PI (CN) using encrypted and password protected file. As soon as the 3-month follow-up is completed (within 6 months of the study start date), the Study Register linking identifiable data with the questionnaire data is destroyed at the clinical site.

Data is analysed using SPSS software V27, the database is stored in a UCC icloud (one drive). Once data is entered and verified, all paper questionnaires and study register are destroyed. Only the study team have access to the data.

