### Analysis

Data analysis uses descriptive statistics. Categorical data is presented as proportions and percentages, continuous data as medians inter quartile ranges. Non-parametric paired statistics is used to compare the pre and post data, however sample size is too small for a comprehensive analysis.

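### The August–October 2023 window for the three-month follow-up does not follow from March–June baselines, which give June–September

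*Combined protocol and SAP*

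**What the plan says.** Study Design describes a one-group pre-post study with surveys at baseline, 1 month and 3 months. Recruitment, baseline data and the intervention fall in March–June 2023, followed by "1 month follow-up April to July and three month follow-up August to October 2023".

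The first Data collection section states how follow-up is done: "The one-month and three month follow-up via telephone or in the OPD clinic", or at home, within the usual visit schedule. It adds "No extra clinic or home visits are planned as part of the study". It gives no tolerance around either time point.

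Under Outcomes, "The 3-month questionnaire repeated the baseline measures and adherence questions". The study log described at the end of that section covers invitations, refusals and their reasons, and then "number of patients who consented, number of patients who completed 1-month and 3-month follow-up". It lists counts and mentions no dates.

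Analysis states "Non-parametric paired statistics is used to compare the pre and post data". Data management contains a second timing statement for the same assessment: "As soon as the 3-month follow-up is completed (within 6 months of the study start date").

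**The concern.** Two windows in one sentence should follow from the same baseline period, and only one does. The 3-month window opens in August, although anyone enrolled in March or April reaches three months before then.

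What is at stake is the meaning of the 3-month label. The exercise and leaflet-adherence items ask about the past 7 days, and the protein item asks about the previous day. A late assessment therefore describes behaviour at the date it was made, not at three months. If early enrollees wait until August, results at four to five months are mixed with results at three months. This would touch the 3-month part of objective (e), objective (f) on repeat frailty screening and health, and the paired comparison. The design has no control group and the target is small ("We aim to recruit 15-20 patients to test the feasibility of the intervention in this population"), so a few off-schedule patients could be a visible share of the data.

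**Working it through.** **Inputs** (all from Study Design): baselines March–June 2023; follow-up at 1 and 3 months; stated windows April–July and August–October 2023. Only months are given, so the first and last day of each month are used as limits.

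**Step 1: reproduce the 1-month window.** Window = baseline period + 1 month. March–June + 1 month = April–July. This matches the plan.

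**Step 2: apply the same rule at 3 months.** March–June + 3 months = June–September (1 June to 30 September 2023). The plan says August–October, so the stated window opens two months late and closes one month late.

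**Step 3: try other readings.**
- Three months after the 1-month contact: April–July + 3 months = July–October. The end matches, the start does not.
- Baseline + 4 months = July–October. Same result.
- Baseline + 5 months = August–November. The start matches, the end does not.
- Working back: August–October − 3 months = May–July, which is not the stated baseline period.

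No single offset can succeed, because a baseline period of four calendar months cannot map onto a follow-up window of three.

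**Step 4: consequence if the stated window is followed.** Days from baseline to the opening of the window = 1 August − baseline date.

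| Baseline | Days to 1 August 2023 | Three calendar months falls on | Earliest assessment |
|---|---|---|---|
| 1 March | 153 | 1 June | 61 days late |
| 31 March | 123 | 30 June | 32 days late |
| 1 April | 122 | 1 July | 31 days late |
| 30 April | 93 | 30 July | 2 days late |
| 1 May | 92 | 1 August | on time |
| 30 June | 32 | 30 September | on time possible |

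The March and April figures are minimum intervals. Late-April enrollees lose only days; the material delay is for March and early April.

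**Step 5: the 6-month statement in Data management.** The study start date is not defined. Assuming it means first enrolment in March, 6 months ends between 1 September (start on 1 March) and 30 September (start on 31 March). The stated window closes on 31 October, which is 60 to 31 days later. A June–September window closes on 30 September, 29 to 0 days later. Most of this second mismatch therefore comes from the window itself.

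**The case against.** The best defence is that the months are a planning calendar. Study Design names the assessments by their interval before it gives dates, telephone contact is allowed, and no section says that a participant due in June or July must wait until August. This stands as a limit on the harm. A reader might infer that early enrollees will be assessed late; the documents show only that they would be if the calendar overrides the interval. It does not remove the error. Routine-visit scheduling does not explain the later window either: no tolerance is stated, and the 1-month window carries no such slack.

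A reader might also infer that the true interval could never be recovered. The documents do not support that. The questionnaire and the study register are not reproduced, and either may carry dates. What can be said is that no section requires the interval to be recorded or reported.

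Nor do the documents show that linkage between baseline and follow-up would be lost. Data management ties destruction of the register to completion of the 3-month follow-up, and later to data entry and verification. The 6-month phrase is a parenthesis beside those conditions and needs only to be aligned with them.

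Finally, which dates are wrong is not proved. August–October would fit May–July baselines. The matching April–July window points to the 3-month dates as the error, but only the sponsor can confirm this.

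**Conclusion.** The concern holds as a wrong stated window of minor severity. With March–June baselines, the 3-month follow-up falls in June–September 2023. The mismatch is certain from the plan's own dates. The delay in Step 4 is conditional on the stated window being followed, and the number of patients affected is unknown because the pattern of accrual is not given.

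The reach is limited. The analysis is descriptive, the plan itself concedes that the sample is too small for a comprehensive analysis, no sample-size figure uses these dates, and objectives (b) to (d) are not materially affected. The conflict with the 6-month limit is secondary and rests on the assumption that the study starts with first enrolment in March.

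**What to change.** - In Study Design, reconcile the dates. If the March–June baselines stand, the 3-month window becomes June–September 2023.
- Time the 3-month assessment from each participant's own baseline, using the telephone or routine contact that the first Data collection section already allows.
- Record the date of each assessment, for example in the study log under Outcomes.
- Report the median and range of the actual interval beside the 3-month results. If follow-up is already finished, this is still worthwhile wherever dates survive.
- In Data management, say what the study start date is and align the 6-month limit with the corrected window.

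The cost is a few sentences of wording, one recorded date per assessment and one reported interval. The downside is that, with no extra visits planned, some 3-month assessments may move to telephone, including the Clinical Frailty Scale, which rests on the rater's judgement.

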### Intervention components

The intervention is delivered by the candidate ANP who is an experienced mental health nurse and is skilled in using motivational interviewing principles to support behaviour change. A normal part of the role is the provision of general health promotion advice for patients in clinics and their home. This aligns with the HSE policy on Making Every Contact Count (<https://www.hse.ie/eng/about/who/healthwellbeing/making-every-contact-count/>).

- Deliver brief Health Promotion advice on exercise and protein nutrition for muscle health to promote resilience and reduce risk of frailty
- Provide patients with information leaflets and clarify expectations for frequency of exercise (Appendix). The exercise and nutrition advise leaflets are used with permission of Travers et al 2022. Both leaflets were deigned based on extensive public patient involvement with older patients, physiotherapist and dietician. The exercises are low risk (use a chair for balance support, sit to stand exercises). Patients with impaired mobility, using Zimmer frame are excluded from study.
- One-month follow-up is undertaken via telephone (or face-to-face if visit scheduled as part of routine care). The one-month follow-up is to encourage adherence to

exercise and nutrition advice and examine adherence and feasibility of undertaking exercise and following diet advice.

#### Data collection

The ANP completes the structured questionnaire with the patient in the MH clinic or patient home during routine clinical consultations. The one-month and three month follow-up via telephone or in the OPD clinic/persons' home as part of normal schedule of visits. No extra clinic or home visits are planned as part of the study.

The structured questionnaire used in this study has been developed by an expert group of geriatricians, and old age psychiatry and includes validated measures of frailty (see below)

This study tests the user acceptability of the intervention and the recruitment and data collection approach.

Ethical approval was obtained from Clinical Research Ethics Committee of the Cork Teaching Hospitals (CREC)

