### Aim

The aim of this study is to test the delivery of brief health promotion advice with supporting information leaflets as part of standard clinical consultation for older people attending a community mental health service.

Objectives: The main objectives are to;

- (a) to screen MH patients for frailty using validated tools the clinical frailty scale and SCAR-F
- (b) to test the feasibility of patient recruitment and data collection in the target population
- (c) determine the prevalence of frailty in older adults living with a mental health condition within an outpatient MH service
- (d) examine the acceptability of the brief health promotion advice and information leaflets as part of MH consultation
- (e) examine self-reported adherence to the exercise and nutrition advice at 1 and 3-month follow-up
- (f) Repeat frailty screening and overall physical and mental health at three month follow-up

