#### Data Collection

Following consent the patient participates in face-to-face interviews with the ANP where a structured questionnaire will be completed (there are no qualitative interviews). The questionnaire has been developed by an expert group of geriatricians, and old age psychiatry.

Data collection includes socio-demographic details, MH diagnosis, co-morbidities,

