#### Outcomes:

Sarcopenia: The SARC-F (tool title not an abbreviation) is a screening tool for sarcopenia ((Malmstrom et al 2013). SARC-F comprises five components using self-report on: strength, assistance walking, rise from a chair, climb stairs, and falls. SARC-F scale scores range from 0 to 10 (i.e. 0–2 points for each component; 0 = *best* to 10 = *worst*) and are dichotomized to represent symptomatic (4+) vs. healthy (0–3) status (Malmstrom et al 2016).

Frailty: Clinical Frailty Scale (CSF) is a judgement-based frailty tool that evaluates specific domains including comorbidity, function, and cognition to generate a frailty score ranging from 1 (very fit) to 9 (terminally ill), a higher score indicates poorer physical and cognitive function (Rockwood et al 2005, Church 2020).

The Global Physical Health Scale v1.2 is a four-item validated general health questionnaire (Riley et al 2010, Hays et al 2015). Four items are used to assess global physical health. Three items (rate your physical health, everyday activities, rate your fatigue) of these are administered using five-category response scales. Higher scores indicated better health. One item (rating of pain on average) uses a response scale of 0–10 that is recoded to five categories (0 = 1; 1-3 = 2; 4-6 = 3; 7-9 = 4; 10 = 5), the scale is then reverse coded, i.e. 0 (no pain) = 5). Overall scores range from 5 to 20 indicating best possible physical health (PROMIS 2021)

Mental health: Bespoke mental health items. Two items (rate your overall mental health, rate your mood (sense of well-being) over past seven days) were rated on a 5 point scale (excellent = 5; very poor = 1). Items are presented separately, scores range from 1 to 5, higher score indicates better mental health.

Exercise: Two items from Yale Physical Assessment Scale (vigorous exercise frequency and duration over past 7 days, and Walking for exercise frequency and duration over past 7 days) ((De Abajo et al., 2001). Frequency was rated on a 4 point scale (not at all=0; 1-2 times=1, 3-4 times=2 or >4 times=3) Duration (0=not applicable, 1=10-30 mins, 2=31-60 mins, 3> 60 mins. Scores are calculated by multiplying Frequency score X Duration score (no weight was applied). Higher scores indicate more activity. Items were not combined for an overall exercise score.

Post intervention, we added an additional question specific to the exercises on the information leaflet

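### The judgement-based Clinical Frailty Scale is scored face to face at baseline but may be scored by telephone at three months; the plan pools both modes and does not provide for recording which was used

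*Combined protocol and SAP*

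**What the plan says.** **Design.** Under Study Design: "The study uses a one group pretest"–posttest layout, with surveys at baseline, one month and three months. There is no control group.

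**Baseline mode.** The Data Collection section that follows Obtaining Consent states: "Following consent the patient participates in face-to-face interviews with the ANP where a structured questionnaire will be completed". The Data collection section that precedes Obtaining Consent gives the setting: "The ANP completes the structured questionnaire with the patient in the MH clinic or patient home during routine clinical consultations".

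**Follow-up mode.** That same earlier section continues: "The one-month and three month follow-up via telephone or in the OPD clinic", or the patient's home, within the usual visit schedule. It adds: "No extra clinic or home visits are planned as part of the study".

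**Instrument.** Outcomes says of the CFS that it "is a judgement-based frailty tool that evaluates specific domains including comorbidity, function, and cognition", on a scale from 1 to 9. Objective (f) under Aim is: "Repeat frailty screening and overall physical and mental health at three month follow-up". Outcomes confirms that the three-month form takes the baseline measures again, together with items on adherence.

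**Analysis.** Pre and post data are compared with paired non-parametric statistics. The section does not mention mode of assessment and concedes that the numbers do not allow a full analysis.

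**Records.** The study log described at the end of Outcomes covers invitations, refusals and their reasons, consents and completed follow-ups. Mode of follow-up is not on the list. Under Data management, the paper questionnaires and the study register are destroyed once data are entered and verified.

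**The concern.** The CFS score is the assessor's reading of the patient. In person the nurse can see the patient move and the setting they are in; by telephone the nurse depends on what is said. If the two modes give systematically different scores, baseline carries none of that difference and three months carries it for every patient telephoned. With one group, nothing cancels it.

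At stake is what the pre/post frailty comparison under objective (f) can support. A reader shown a CFS change could not tell how much of it came from a change in how the scale was taken. If mode is not captured at the time, the loss may be permanent, because the source forms are destroyed. SARC-F is less exposed, since Outcomes describes it as self-report.

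**Working it through.** The plan gives no figure that depends on mode. The target of 15–20 patients under Sample size has no effect size, standard deviation or power behind it, so there is nothing to reproduce. The check is a comparison of sections, followed by an illustration.

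**Sections side by side**

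| Question | Answer in the plan | Where |
|---|---|---|
| Baseline mode | Face to face, clinic or home | Both data collection sections |
| Three-month mode | Telephone, clinic or home | Data collection (before Obtaining Consent) |
| Is the CFS repeated at three months? | Yes | Aim, objective (f); Outcomes |
| Must the three-month CFS be in person? | Not stated | – |
| Telephone scoring procedure for the CFS | None | – |
| Is mode recorded? | Not provided for; absent from the study log | Outcomes |
| Analysis by mode | None | Analysis |

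The later Data Collection section refers to interviews in the plural, which could be read to cover follow-up as well. The earlier section expressly allows the telephone at three months, so the risk remains; the two should be reconciled.

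**Illustration (assumed values)**

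Let p be the share of pairs whose three-month CFS is by telephone, and d the mean telephone-minus-in-person difference in score. Because every baseline is in person,

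observed mean change = true mean change + p × d.

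- p = 0.25, d = 0.25: 0.25 × 0.25 = 0.06 points
- p = 0.5, d = 0.5: 0.5 × 0.5 = 0.25 points
- p = 0.75, d = 1: 0.75 × 1 = 0.75 points

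The plan names no specific paired test, so I used an exact sign test as a stand-in. With no true change and k one-point shifts all in one direction, two-sided P = 2 × 0.5^k:

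- k = 3: 0.25
- k = 5: 0.0625
- k = 6: 0.031

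Six shifts in the same direction are therefore needed for a nominal result at 0.05. If each telephone score has chance q of being one point lower and nothing else varies, the number of shifts among n pairs is binomial with probability p × q:

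| p | q | p × q | P(≥ 6 shifts), n = 15 | P(≥ 6 shifts), n = 20 |
|---|---|---|---|---|
| 0.5 | 0.25 | 0.125 | 0.007 | 0.031 |
| 0.5 | 0.5 | 0.25 | 0.148 | 0.383 |
| 0.75 | 0.5 | 0.375 | 0.517 | 0.821 |

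A milder assumption is that 10 of 20 patients are telephoned and 10–30% of those are scored one level off. That gives 10 × 0.1 = 1 to 10 × 0.3 = 3 patients, or 5–15% of the sample. Even if all three moved the same way, the sign test would give P = 0.25.

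The effect therefore runs from negligible to enough to produce a nominal change. The plan supplies neither p, d nor q.

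**The case against.** The best case for leaving the plan alone has four parts.

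1. **Purpose.** This is a feasibility study of 15–20 people. Objective (f) is worded as repeating the screening, not as estimating an effect, and the Analysis section disclaims a full analysis. This stands as a limit on importance. It does not remove the point: a paired comparison is still planned, and the plan says it is testing its own approach to data collection. How often the telephone was used is part of that result.

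2. **Frequency.** Intervention components makes the telephone the default only for the one-month contact, and that questionnaire concerns acceptability and ease of use. Telephone scoring of the CFS at three months may be rare. This stands: the plan permits it but does not say how common it will be.

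3. **Validity by telephone.** The CFS is described as a judgement, not a performance test, and the nurse may know the patients from her or his own caseload. Nothing in the documents says telephone scoring is less valid. This stands, and it is why the direction and size are left open.

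4. **Noise or bias.** Error without a direction adds scatter, not systematic shift, and in-person scores carry error too. This also stands; only a systematic excess would bias the change.

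A reader might also infer that mode follows how unwell the patient is, since it depends on the routine visit schedule. No section says so, and enrolment is limited to patients judged stable. It is a possibility only.

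Another tempting inference is that the nurse's knowledge of adherence could be neutralised by scoring the CFS first. The same nurse delivers the advice and examines adherence at one month, so question order at three months cannot hide it. Data management already discloses that the data collector is unblinded.

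**Conclusion.** The point holds as a design risk of unknown size and direction. The plan allows a change in mode between baseline and three months for a judgement-based scale. It pools the modes in a single-group comparison and makes no provision to record them, so a mode effect could not be separated from change in CFS. If no three-month CFS is taken by telephone, the risk is nil.

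Two stronger readings are not supported. One is that the CFS change will be biased: that needs a systematic difference between modes and enough telephone assessments, and the documents establish neither. The other is that mode-related shifts would rival the true three-month change: the documents give no expected change to compare with.

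The figures of 0.06 to 0.75 points and the sign-test probabilities rest wholly on assumed values and show range only. In each row of the binomial table the expected share of shifted pairs is at most 0.375, below half. The median paired change, the type of summary the plan favours, would on average stay at zero even where the test turned nominally significant. The matter is minor for the study's conclusions, but nearly free to correct.

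**What to change.** - **Data collection.** State that the three-month CFS is scored at a routine clinic or home visit whenever one falls within the stated three-month follow-up window (August to October under Study Design), and by telephone only otherwise. No visits are added. Tie the rule to the window, not to the visit nearest the due date: patients enrolled in March or April reach three months in June or July, before the window opens. Reconcile the wording with the later Data Collection section.
- **Questionnaire and dataset.** Add a field for mode of assessment and enter it in the dataset before the paper forms are destroyed under Data management.
- **Analysis.** Report CFS change for all pairs, and show face-to-face and telephone pairs separately beside it. Do not restrict the headline to face-to-face pairs. If mode were related to patient status, that would exchange a measurement problem for a selection problem. If half were telephoned, it would also leave about 10 of 20 pairs, or 7–8 of 15.
- **Feasibility.** Report the number assessed by each mode as a result under objective (b).

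The cost is one form field and an extra table row. The split groups will be very small and can only be descriptive.
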